### 12.6.4 Other Planned Analyses

Summary tables (descriptive statistics and/or frequency tables) will be provided for all baseline, efficacy, and safety variables (i.e., treatment-related or serious adverse events), as appropriate. Frequency counts and percentage of subjects within each category will be provided for categorical data. Measures of central tendency (mean, median and mode), measures of variability and dispersion (standard deviation, range and quantiles) will be calculated for continuous

variables. Chi-square or Fisher exact test will be used to detect the difference of percentage between treatment arms. Kruskal-Wallis rank sum or ANOVA analyses will be performed to test the homogeneity of continuous variables between groups. All variables will be examined for normality and transformed as needed prior to analysis.

#### 12.7 Criteria for Stopping Study

The study will include an initial safety run-in portion. Patients in the safety run-in will be monitored through completion of induction durvalumab, chemoradiation, and 2 cycles of consolidation durvalumab for assessment of safety prior to completion of enrollment.

If 3 out of the first 5 patients or 4 out of the first 10 patients experience dose limiting toxicities (DLT), further enrollment will be halted and subsequent accrual re-evaluated with investigators and sponsor-investigator. Patients in the safety run-in phase will be analyzed for PFS and outcomes as members of the full study cohort.

The stopping rule criterion was based on the sequential probability ratio test  $H_0$ : DLT rate = 10% vs  $H_1$ : DLT rate = 30%, given type I error of 0.05 and power 0.8.

Enrollment will thus first be paused after the first 5 patients are enrolled and complete the above safety window. If stopping criteria are not met, enrollment will then continue with another pause after 10 total patients are enrolled and complete the above safety window. If stopping criteria are not met, enrollment will then continue for the full planned cohort.

Patients in the safety run-in phase will be analyzed for PFS and outcomes as members of the full study cohort.

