### 5.4 Safety Run In-Portion

This study will include an initial safety run-in portion. The dose limiting toxicity (DLT) period is through completion of induction durvalumab, chemoradiation, and 2 cycles of consolidation durvalumab. Enrollment will pause after the first 5 patients are enrolled. If 3 out of the first 5 patients experience dose limiting toxicities during the DLT period, further enrollment will be halted, and subsequent accrual re-evaluated with site investigators and the sponsor-investigator. If stopping criteria are not met, enrollment will continue, and accrual will again pause after 10 total patients are enrolled.

If 4 out of the first 10 patients experience dose limiting toxicities (DLT) during the DLT period, further enrollment will be halted, and subsequent accrual re-evaluated with site investigators and the sponsor-investigator. If stopping criteria are not met, enrollment will then continue for the full planned cohort. Patients in the safety run-in phase will be analyzed for PFS and outcomes as members of the full study cohort.

Subjects in the safety run in group who do not remain on the study through completion of the DLT period for reasons other than DLT will be replaced with another subject.

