### 13. TRIAL MANAGEMENT

#### 13.1 Data and Safety Monitoring Plan (DSMP) HCRN

oversight activities include:

- Review and processing of all adverse events requiring expedited reporting as defined in the protocol
- Provide trial accrual progress, safety information and data summary reports to the sponsor-investigator
- Submit data summary reports to the DSMB for review according to DSMB Charter

This study will have a Data and Safety Monitoring Board (DSMB). The DSMB is chaired by an independent medical oncologist external to this trial. The DSMB will provide a recommendation to the sponsor-investigator after all information is reviewed. This information will also be provided to HCRN who will distribute to the site investigator/participating sites for submission to their respective IRB according to the local IRB's policies and procedures.

The DSMB review will include but is not limited to:

- Adverse event summary report
- Audit results if applicable

- Data related to stopping/decision rules described in study design
- Study accrual patterns
- Protocol deviations

The DSMB will meet after the first 5 patients are enrolled and have completed 2 cycles of consolidation durvalumab, or after 3 patients of the first 5 in the safety run-in cohort have experienced DLT (whichever comes first), to review data for stopping rules as above. The DSMB will again meet after the first 10 patients are enrolled and have completed 2 cycles consolidation durvalumab, or after 4 patients of the first 10 in the safety run-in cohort have experienced DLT (whichever comes first), to review data for stopping rules as above. Additional DSMB meetings may be convened upon request of the sponsor-investigator, DSMB, or other applicable oversight body.

After the safety lead-in period, the next regular meeting will occur within 6 months of the 11th subject beginning study drug administration. The DSMB will continue to meet approximately every 6 months during the active study drug administration of the study. At the discretion of the DSMB, they may meet more frequently during the course of the study, as more data becomes available. The timing of the next scheduled meeting will be documented in the minutes from the prior meeting.

The DSMB will review the data regularly until at least 100 days after the last participant goes off study treatment. At this point, the DSMB will conduct reviews as needed until the study terminates.

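### The DLT stopping rule cites an SPRT with power 0.8 at a 30% DLT rate, but as applied at 5 and 10 patients it triggers with probability 0.373

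*Combined protocol and SAP*

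**What the plan says.** Section 12.7 gives the origin of the rule: "The stopping rule criterion was based on the sequential probability ratio test", with a null DLT rate of 10% and an alternative of "DLT rate = 30%, given type I error of 0.05 and power 0.8". The rule is applied twice. Three DLTs in the first 5 patients halt enrollment, and Section 5.4 states the second look: "If 4 out of the first 10 patients experience dose limiting toxicities (DLT) during the DLT period, further enrollment will be halted". After a halt, accrual is re-evaluated with the investigators. After the second look, Section 12.7 says: "If stopping criteria are not met, enrollment will then continue for the full planned cohort". Section 12.3 sets that cohort at 54, so up to 44 patients follow the run-in.

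Oversight after patient 10 is in Section 13.1. The DSMB's remit includes "Data related to stopping/decision rules described in study design"; "the next regular meeting will occur within 6 months of the 11th subject beginning study drug administration", then about every 6 months; and "Additional DSMB meetings may be convened upon request of the sponsor-investigator, DSMB, or other applicable oversight body". HCRN is to "Submit data summary reports to the DSMB for review according to DSMB Charter". Section 11.3 sends SAE summaries to the sponsor-investigator within 1 business day, and Appendix A sets discontinuation rules for individual patients. The only DLT counts in the protocol are 3 of 5 and 4 of 10.

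**The concern.** The power and type I error of an SPRT depend on continuing to count until one of two boundaries is crossed. Section 12.7 keeps the upper boundary at two looks, drops the lower one, and treats every result below the upper boundary as clearance. The cited 0.05 and 0.8 then no longer describe the rule.

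Safety and feasibility is a primary objective (Section 2.1.1), and this is the protocol's only count-based safety rule. An investigator, IRB or DSMB member who takes 0.8 at face value would think that a regimen with a 30% DLT rate has about a 20% chance of passing the run-in. The real chance is about three times that.

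**Working it through.** **Inputs.** p0 = 0.10, p1 = 0.30, alpha = 0.05, beta = 0.20, cut-offs 3/5 and 4/10 (Section 12.7); total enrollment 54 (Section 12.3). DLT rates below are rates among counted patients, since Section 5.4 replaces run-in patients who leave early without a DLT.

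**1. Reproduce the cut-offs.** Divisor: ln[p1(1−p0)/(p0(1−p1))] = ln(0.27/0.07) = 1.350.

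- Slope: ln(0.9/0.7)/1.350 = 0.1862 per patient.
- Upper boundary: ln(0.80/0.05)/1.350 + 0.1862n = 2.054 + 0.1862n. This is 2.98 at n = 5 and 3.92 at n = 10, so 3 and 4 DLTs. Both match the plan.
- Lower boundary: ln(0.20/0.95)/1.350 + 0.1862n = −1.154 + 0.1862n. This is −0.22 at n = 5 (acceptance impossible) and 0.707 at n = 10 (acceptance only with 0 DLTs).

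**2. The cited power belongs to the continued test.** With both boundaries, a look after every patient and no truncation, the SPRT rejects with probability 0.825 at 30% and 0.036 at 10%. Truncated at 54 patients, it gives 0.816 and 0.035.

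**3. The rule as written.** P(trigger) = P(X5 ≥ 3) + Σ over x = 0, 1, 2 of P(X5 = x) × P(at least 4−x DLTs in the next 5).

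- At 30%: 0.1631 + (0.16807×0.03078 + 0.36015×0.16308 + 0.30870×0.47178) = 0.1631 + 0.2095 = 0.373. Passing probability: 0.627.
- At 10%: 0.0086 + (0.59049×0.00046 + 0.32805×0.00856 + 0.07290×0.08146) = 0.0086 + 0.0090 = 0.018.
- By the same formula: 0.138 at 20%, 0.636 at 40%.

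**4. What a pass means.** At 30%, 0 DLTs in 10 has probability 0.7^10 = 0.028, so passing with 1 to 3 DLTs has probability 1 − 0.373 − 0.028 = 0.599. At 10% it is 1 − 0.018 − 0.349 = 0.634. In that range the SPRT is undecided at n = 10 and would call for more patients.

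**5. Ten patients cannot deliver the cited figures.** The smallest single-look exact test with alpha ≤ 0.05 and power ≥ 0.8 needs 25 patients, rejecting at 6 or more DLTs (0.033 and 0.807).

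**6. The same boundary carried forward.** It is 5.78, 7.64 and 9.50 at n = 20, 30 and 40, so 6, 8 and 10 DLTs. Cumulative trigger probability, exact, in enrollment order:

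| DLT rate | Looks at 5 and 10 | By 20 | By 30 | By 40 |
|---|---|---|---|---|
| 10% | 0.018 | 0.024 | 0.028 | 0.029 |
| 15% | 0.061 | 0.100 | 0.126 | 0.144 |
| 20% | 0.138 | 0.243 | 0.321 | 0.381 |
| 25% | 0.245 | 0.433 | 0.563 | 0.655 |
| 30% | 0.373 | 0.625 | 0.770 | 0.855 |

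**7. Sensitivity to how patients are counted.**

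- *Date of becoming evaluable.* A DLT counts on the day it occurs, while a patient without one waits out the window, so early tallies over-represent DLTs. Simulation (20,000 runs per setting) assumed uniform DLT onset, a window of 4.0 or 6.1 months, and 3 or 5.4 patients per month. The cumulative trigger was about 0.05 to 0.13 at a 10% rate and 0.52 to 0.75 at 20%.
- *Non-completers.* Suppose, as an assumption, that 20% of patients without a DLT leave early and are not counted. A 10% rate among enrolled patients becomes 0.10/(0.10 + 0.90×0.80) = 0.122 among counted patients, and the five-look trigger rises from 0.029 to 0.065. A 30% rate becomes 0.30/(0.30 + 0.70×0.80) = 0.349, and the current two-look trigger becomes 0.504, still well below 0.8.

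**The case against.** The best defense is the wording. Section 12.7 says that the criterion was based on an SPRT with these parameters, and the cut-offs match that test exactly. It does not literally say that two looks have power 0.8. A 10-patient run-in is a legitimate screen for gross toxicity. This stands, and it rules out one tempting inference: the cut-offs are not miscalculated. But 0.05 and 0.8 are the only operating characteristics the plan gives for the rule, so a reader will take them as the rule's own.

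A second defense is continuing oversight: regular and ad hoc DSMB meetings, rapid SAE summaries and individual discontinuation rules. A reader might infer that the 44 later patients go unmonitored, or that no later threshold exists anywhere. The documents support neither. What can be said is that the protocol text states no DLT count after patient 10; the Charter may. Oversight by judgment does not, however, give the two-look rule the power cited for it.

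Third, added triggers may bring little practical gain. This also largely stands. At 54/18 = 3 patients per month, the scheduled DSMB meeting falls at the latest at 11 + 6×3 = 29 enrolled. In trials at a 30% rate that pass the run-in and later trigger, the simulated median trigger falls at 29 to 33. An obligatory review would therefore not be an earlier one, and no saving in enrollment can be claimed.

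**Conclusion.** The point holds as a misdescription of the rule. Section 12.7 attaches type I error 0.05 and power 0.8 to a rule whose trigger probabilities are 0.018 at 10% and 0.373 at 30%. A regimen at the plan's own unacceptable rate passes with probability 0.627, where a power of 0.8 implies 0.20. These are exact binomial results. They assume independent patients, a common DLT rate among counted patients, and 5 and 10 evaluable patients at the two looks.

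A reader might go further and conclude that the trial must add main-phase stopping limits. The documents do not support that. A short run-in followed by DSMB review is a defensible design, and whether to add later count triggers is the sponsor's choice. What the sponsor should not leave in place is a stated property that the rule lacks. This is worth correcting, but it does not by itself make the trial unsafe.

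**What to change.** **Main change, Section 12.7.** Replace the type I error and power as the description of the rule with its own trigger probabilities, 0.018 at a 10% DLT rate and 0.373 at 30%. State that 3/5 and 4/10 are points on an SPRT upper boundary truncated at 10 patients. If the DSMB Charter already holds a main-phase DLT threshold, refer to it here. The cost is a sentence or two.

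**Optional, if the sponsor wants to reach the cited power.** In Sections 12.7 and 13.1, add an unscheduled DSMB review at 6 DLTs in the first 20 patients, 8 in the first 30 or 10 in the first 40, run-in patients included.

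- Count strictly in order of enrollment, never by date of becoming evaluable.
- Replace patients who leave early without a DLT by the next enrolled patient, as in Section 5.4. The figures of 0.855 at 30% and 0.029 at 10% hold if leaving early is unrelated to DLT status. If only patients without a DLT drop out of the count, trigger rates are higher, as shown above.
- Let the DSMB decide whether enrollment pauses.

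This costs a paragraph and a running DLT tally from adverse event data already recorded. The downside is more reviews at intermediate rates: 0.381 against 0.138 now at 20%, and 0.655 against 0.245 at 25%. Such rates may be common, because Section 5.4.1 counts any febrile neutropenia and most Grade 3 or higher non-immune events during chemoradiation, and the documents give no background DLT rate. That is why the trigger should be a review and not an automatic halt.

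### Section 12.7 gives the DLT stopping rule a power of 0.8, but the rule ends at 10 patients and halts with probability 37.3% at the 30% DLT rate it is meant to detect (1.8% at 10%)

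*Combined protocol and SAP*

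**What the plan says.** Section 12.7 of the combined protocol and SAP sets two numerical triggers, 3 DLTs among the first 5 patients and 4 among the first 10. If either is met, "further enrollment will be halted and subsequent accrual re-evaluated with investigators and sponsor-investigator". On the origin of these limits it says: "The stopping rule criterion was based on the sequential probability ratio test", with a null DLT rate of 10% and an alternative of 30%, "given type I error of 0.05 and power 0.8". No other error rates are given for the rule.

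Section 5.4 repeats the triggers and the pauses at 5 and 10 patients. On passing the second pause: "If stopping criteria are not met, enrollment will then continue for the full planned cohort". Run-in patients who leave before the end of the DLT period "for reasons other than DLT will be replaced with another subject", so the denominators are 5 and 10 evaluable patients.

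Section 13.1 ties two DSMB meetings to the same counts, each held early if its count is reached early. After that the DSMB meets about every 6 months. The protocol states no DLT boundary for those later meetings.

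**The concern.** Wald's SPRT has a continuation zone between an upper and a lower boundary, and its nominal error rates hold only if sampling goes on until one boundary is crossed. Section 12.7 uses only the upper boundary, looks at it twice, and treats every count below it at patient 10 as a pass. That is a different procedure, and most of the power of the SPRT comes from patients it never tests.

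Safety is a primary objective (Section 2.1.1), and passing the run-in opens accrual from 10 to the planned 54. An investigator, IRB or DSMB member who takes 0.8 as the chance of halting at a 30% DLT rate will read too much into a pass.

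**Working it through.** **Inputs.** Null rate 0.10, alternative 0.30, nominal errors 0.05 and 0.8, limits 3/5 and 4/10, no later limit (Sections 12.7 and 5.4). DLTs are taken as independent and the limits as 'at least'.

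**1. Reproduce the limits.** The SPRT rejects 10% when r·ln(0.3/0.1) + (n − r)·ln(0.7/0.9) ≥ ln(0.8/0.05). That is 1.0986r − 0.2513(n − r) ≥ 2.7726, or r ≥ (2.7726 + 0.2513n)/1.3499.

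- n = 5: r ≥ 2.98, so 3.
- n = 10: r ≥ 3.92, so 4.

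Both limits in the plan are right.

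**2. Where 0.05 and 0.8 belong.** Run patient by patient until a boundary is crossed, this SPRT rejects with exact probability 0.0356 at 10% and 0.8247 at 30%. The stated figures fit that test. Its lower boundary is ln(0.2/0.95) = −1.558, which at n = 10 is r ≤ 0.71. On the count at patient 10, then, only 0 DLTs would favour 10%. Counts of 1, 2 or 3 mean 'continue testing', yet the plan passes them. An SPRT cut off at 10 patients is still undecided with probability 0.504 at 10% and 0.545 at 30%.

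**3. The rule as written.** Let X be the DLTs in patients 1–5 and Y those in patients 6–10.

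P(halt) = P(X ≥ 3) + P(X=0)·P(Y ≥ 4) + P(X=1)·P(Y ≥ 3) + P(X=2)·P(Y ≥ 2)

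- At 10%: 0.00856 + 0.59049×0.00046 + 0.32805×0.00856 + 0.0729×0.08146 = 0.00856 + 0.00902 = **0.0176**.
- At 30%: 0.16308 + 0.16807×0.03078 + 0.36015×0.16308 + 0.3087×0.47178 = 0.16308 + 0.20954 = **0.3726**.

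| True DLT rate | First look | Second look | P(halt) |
|---|---|---|---|
| 10% | 0.0086 | 0.0090 | 0.0176 |
| 20% | 0.0579 | 0.0797 | 0.1377 |
| 30% | 0.1631 | 0.2095 | 0.3726 |
| 40% | 0.3174 | 0.3182 | 0.6356 |
| 50% | 0.5000 | 0.3379 | 0.8379 |

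Simulation with 1,000,000 runs per rate agrees (0.0176, 0.1376, 0.3719, 0.6363, 0.8378). P(halt) reaches 0.50 at a DLT rate of 34.7% and 0.80 only at 47.7%.

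**4. Is it the number of looks or the early end?** Checking the upper boundary after every patient up to 10 gives the same 0.0176 and 0.3726. The early DSMB triggers in Section 13.1 therefore add nothing, and the shortfall comes from ending at 10. For comparison, applying the same upper boundary every 5 patients would give power of 0.787 by 30 patients and 0.868 by 40.

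**5. Could other limits at 5 and 10 deliver 5% and 80%?** No. At a 10% rate, a first limit of 2 or fewer already halts with probability at least 0.0815, and a second limit of 3 or fewer gives at least 0.0702. Both exceed 0.05. The first limit must therefore be at least 3 and the second at least 4, and raising either one lowers power. The plan's own pair is the most powerful that respects 5%, at 37.3%. Power above 80% appears with a second limit of 2 of 10 (0.8507), where the halting probability at a 10% rate is 0.2639.

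**The case against.** The strongest reply is grammatical. The criterion is said to be based on an SPRT, so 0.05 and 0.8 can be read as inputs to the boundary, and step 1 shows that they yield exactly 3/5 and 4/10. On that reading nothing was miscalculated. The reading is possible, and the proposed wording adopts it. It does not rescue the text as it stands, because these are the only error rates given for the rule and nothing says they stop applying when testing ends at patient 10.

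Three further points stand in whole or in part:

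- The type I error is not a defect. At 1.8% it lies under the 5% ceiling, and only the power falls short.
- The trigger is not the only safeguard. A halt leads to re-evaluation and does not close the trial. The DSMB keeps meeting and may act on fewer DLTs, and every patient given durvalumab is evaluable for toxicity (Section 12.4). The DSMB works to a charter that is not in these documents. This limits the consequences, but discretion has no stated power and cannot supply the missing 0.8.
- A pass is not formally an acceptance of the 10% rate, since Section 12.7 says only that enrollment continues. A comparison of pass probabilities therefore shows how much reassurance a reader might draw and is not a property the plan claims. With errors of 0.05 and 0.2, a pass would be 0.95/0.20 = 4.75 times as likely at 10% as at 30%. Under the rule it is 0.982/0.627 = 1.57 times as likely.

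**Conclusion.** The concern holds. The limits are correct, but the power attached to them is not the power of this rule: 37.3% against a stated 80% at a 30% DLT rate, so such a regimen passes the run-in 62.7% of the time. The type I error is 1.8% against a stated 5%, a departure on the conservative side. The result rests on independent DLTs, limits read as 'at least', and 5 and 10 evaluable patients, which the replacement rule in Section 5.4 supports. It describes the numerical trigger only and counts no discretionary DSMB action. This should be corrected, but it does not call for a different run-in.

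**What to change.** In Section 12.7, replace the sentence that gives the SPRT and its error rates with:

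> The limits of at least 3/5 and at least 4/10 are taken from the upper boundary of an SPRT (10% vs 30%, nominal type I error 0.05 and power 0.8). Because this protocol's numerical testing ends at 10 patients, the rule halts accrual with probability 1.8%, 13.8%, 37.3%, 63.6% and 83.8% at true DLT rates of 10%, 20%, 30%, 40% and 50%, assuming independent DLTs and 5 and 10 evaluable patients. This protocol specifies no numerical DLT boundary after patient 10; later safety review is by the DSMB.

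The cost is that one sentence becomes three. The limits, looks, pauses, sample size, visits and DSMB schedule stay as they are.

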### 13. TRIAL MANAGEMENT

#### 13.1 Data and Safety Monitoring Plan (DSMP) HCRN

oversight activities include:

- Review and processing of all adverse events requiring expedited reporting as defined in the protocol
- Provide trial accrual progress, safety information and data summary reports to the sponsor-investigator
- Submit data summary reports to the DSMB for review according to DSMB Charter

This study will have a Data and Safety Monitoring Board (DSMB). The DSMB is chaired by an independent medical oncologist external to this trial. The DSMB will provide a recommendation to the sponsor-investigator after all information is reviewed. This information will also be provided to HCRN who will distribute to the site investigator/participating sites for submission to their respective IRB according to the local IRB's policies and procedures.

The DSMB review will include but is not limited to:

- Adverse event summary report
- Audit results if applicable

- Data related to stopping/decision rules described in study design
- Study accrual patterns
- Protocol deviations

The DSMB will meet after the first 5 patients are enrolled and have completed 2 cycles of consolidation durvalumab, or after 3 patients of the first 5 in the safety run-in cohort have experienced DLT (whichever comes first), to review data for stopping rules as above. The DSMB will again meet after the first 10 patients are enrolled and have completed 2 cycles consolidation durvalumab, or after 4 patients of the first 10 in the safety run-in cohort have experienced DLT (whichever comes first), to review data for stopping rules as above. Additional DSMB meetings may be convened upon request of the sponsor-investigator, DSMB, or other applicable oversight body.

After the safety lead-in period, the next regular meeting will occur within 6 months of the 11th subject beginning study drug administration. The DSMB will continue to meet approximately every 6 months during the active study drug administration of the study. At the discretion of the DSMB, they may meet more frequently during the course of the study, as more data becomes available. The timing of the next scheduled meeting will be documented in the minutes from the prior meeting.

The DSMB will review the data regularly until at least 100 days after the last participant goes off study treatment. At this point, the DSMB will conduct reviews as needed until the study terminates.

